## 5. Objectives and Endpoints

## 5.1. Objectives

#### 5.1.1. Primary Objective(s)

To demonstrate an improvement from baseline to 3 months post radiofrequency ablation in worst pain score in the past 24 hours in subjects treated for metastatic lesions in only the thoracic and/or lumbar vertebral body(ies).

Worst pain score at the target treatment site will be collected from the Brief Pain Inventory (BPI).

[figure not shown]
### 5.1.2. Secondary Objective(s)

To characterize change from baseline to 3 months post radiofrequency ablation in worst pain score in the past 24 hours in subjects treated for metastatic lesions in the periacetabulum, iliac crest, and/or sacrum, and for benign bone tumors.

Worst pain score at the target treatment site will be collected from the BPI.

#### 5.1.3. Additional Measures

•

#### 5.1.4. Safety Measure

To characterize incidence of all device, procedure and/or therapy related adverse events and device deficiencies from enrollment to the 12-Month Visit.

## 5.2. Endpoints

### 5.2.1. Primary Endpoint

The primary endpoint of the study is the improvement of worst pain score at the target treatment site 3 months post RF ablation for subjects with metastatic lesions in only the thoracic and/or lumbar vertebral body(ies).

#### 5.2.2. Secondary Endpoints

The secondary endpoint of the study is to characterize change in worst pain score at the target treatment site 3 months post RF ablation for subjects with metastatic lesions in the periacetabulum, iliac crest, and/or sacrum, and/or for benign bone tumors.

#### 5.2.3. Additional Measures

## 6. Study Design

This is a prospective, multi-center, non-randomized, post-market, single arm study designed to provide effectiveness outcomes on the Medtronic OsteoCool™ RF Ablation system.

The study will evaluate up to 250 subjects at approximately 20 study sites in the United States (US), Europe (EUR), and Canada (CAN). Patients that meet all inclusion criteria, do not meet any exclusion criteria, and provide written informed consent (IC) will be enrolled in the study. Commercially available study devices will be used within the intended approved indication as listed in the IFUs applicable in each country/region.

Figure 6-1 outlines the study design and required follow-up requirements.

#MDT16075 Version 4.0

Page 24 of 81

Figure 6-1: Study Design

#### **Enrollment**

Obtain informed Consent

#### **Baseline**

Verify eligibility criteria, obtain pregnancy test
collect demographic, cancer history, baseline images at the target
site(s) if available, Karnofsy Performance Scale (not for benign bone
tumors), concomitant medications/treatments, BPI, EQ-5D-5L,
EORTC-QLQ-C15-PAL (not for benign bone tumors), reportable adverse
events/device deficiencies and deviations

≤21 days after baseline visit Enrollment, Baseline and RF ablation can occur on the same day

# OsteoCool Procedure Day 0

Collect RF ablation procedure and OsteoCool details, reportable adverse events/device deficiencies, deviations, concomitant medications/treatments, and Generator data uploads

Study Discontinuation No

Was the RF therapy delivered?

#### **Prior to Discharge**

Collect worst pain only, PI's self-assessment on local tumor control, post-treatment images (if available), deviations, and reportable adverse events/device deficiencies

3 days  $\pm$  2 Days after Day 0 1 week (7 days)  $\pm$  2 Days after Day 0 1-Month Visit 30 days  $\pm$ 15 Days after Day 0 3-Month Visit 90 Days  $\pm$  30 Days after Day 0 6-Month Visit 180 days  $\pm$  59 Days after Day 0 12- Month Visit 365 days  $\pm$  90 Days after Day 0

# 3 days, 1 week, 1-, 3-, 6- and 12- Month Visits Post Procedure

Collect reportable adverse events/device deficiencies, deviations, concomitant, PI's self-assessment on local tumor control, medications/treatments, BPI, EQ-5D-5L, EORTC QLQ-C15-PAL (not applicable for benign bone tumors), and follow-up images (if available)

#MDT16075 Version 4.0

Page 25 of 81

#### 6.1. Duration

The start of the study for each subject is defined as the date the subject first signs the informed consent. Enrolled subjects who do not meet baseline eligibility or who do not undergo the OsteoCool procedure will be exited from the study (e.g. RF therapy was not delivered). The completion of the study for each subject is defined as the conclusion of the 12 Month Visit (Study Exit). Each subject's participation in the study is expected to last approximately 1 year from the date of the OsteoCool procedure. Each subject will be evaluated prior to the OsteoCool procedure, during the procedure, prior to hospital discharge, 3 days, 1 week, 1-, 3-, 6-, and 12-months post procedure.

The estimated time needed to enroll all subjects is approximately 3 years. The overall study duration, from first subject enrollment to last subject visit, is expected to last approximately 5 years. The completion of the study is defined as the approval of the Final Study Report and closure of all sites.

#### 6.2. Rationale

The OsteoCool™ RF Ablation system has 510k regulatory clearance in the United States, Conformité Européenne (CE) mark in Europe, and Health Canada License in Canada. The goal of this study is to collect real-world outcomes among a cohort of patients in the US, EUR and CAN with metastatic malignant lesions in a vertebral body, painful metastatic lesions involving bone (in the US, patients with metastatic lesions involving the bone must have failed or were not candidates for standard therapy), and benign bone tumors such as osteoid osteoma who receive treatment with the OsteoCool™ RF Ablation system. Additionally, the study will collect device, procedure and/or therapy related adverse events and device deficiencies. Lastly, subject outcomes (such as pain relief, quality of life, and function) will be evaluated using validated assessment measures. Published data evaluating the real-world use of RF ablation in this patient population is limited. As such, a prospective, single-armed study designed to capture real-world outcomes is justified.

### 7. Product Description

#### 7.1. General

The figure and tables below describe the components of the OsteoCoolTM RF Ablation system.

Any future approved models may be used in the study if commercially available and if the modifications do not have the potential to affect the study results.

#MDT16075 Version 4.0 Page 26 of 81

[figure not shown]

Figure 7-1: OsteoCool™ RF Ablation System

The OsteoCool™ RF Ablation System is comprised of the following main components which are described in Table 7-1 and Table 7-2:

**Table 7-1: General Equipment** 

Products	Model/type	Product Description
OsteoCool™ RF Generator	OC01	Is a coaxial, bipolar RF Ablation platform. It is non-sterile and reusable. RF energy is applied to the subject according to the selected or configured settings. The procedure is automatically monitored, on a per-channel basis, for unexpected responses, which will cause messages to be displayed and RF energy delivery cessation, if appropriate.
OsteoCool™ Cart	OCA01	Is a non-sterile, reusable cart to mount the OsteoCool™ Radiofrequency Generator and OsteoCool™ Peristaltic Pump
OsteoCool™ Desk Stand	OCA02	Is a non-sterile, reusable desk stand to mount the OsteoCool™ Radiofrequency Generator and OsteoCool™ Peristaltic Pump
OsteoCool™ RF Pump Unit and Cable	OC02 – (OC02-R - replacement part only)	Is a non-sterile, reusable pump that circulates sterile water through a closed-loop system during OsteoCool™ radiofrequency (RF) ablation procedures. The OsteoCool™ Peristaltic Pump is suitable for continuous operation.
OsteoCool™ Connector Hub	OC04	Is a non-sterile, reusable cable which provides a path for delivery of radiofrequency (RF) energy and temperature signals to/from OsteoCool™ RF Ablation Probes, OsteoCool™ Independent Thermocouple Monitor, and OsteoCool™ RF Generator.

#MDT16075 Version 4.0 Page 27 of 81

OsteoCool ™ Power	OCE-NEMA515	
Cord North		
America		
OsteoCool ™ Power	OC-CE12350	
Cord Italy		Is the Power Cord for the OsteoCool Radiofrequency
OsteoCool ™Power	OC-BS363	Generator
Cord UK		
OsteoCool ™Power	OC-SEV1011	
Cord Swiss		
OsteoCool ™Power	OCE-CEE7-INT	
Cord Europe		

## **Table 7-2: Consumable, Single Use Devices**

Products	Model/type	Product Description
OsteoCool™ RF	7mm: OCP107;	Is a sterile, single use device that delivers
Ablation Single	OCP-107-INT	Radiofrequency (RF) energy to tissues. This energy is
Probe Kit	10mm: OCP110;	delivered through the probe, which is internally
4 different sizes	OCP110-INT;	cooled. The single kit includes one OsteoCool™ RF
	15mm: OCP115;	Ablation Probe and one OsteoCool™ Tube Kit.
	OCP115-INT	
	20mm: OCP120;	
Out of Continues	OCP120-INT	The dealers of the Control of the Co
OsteoCool™ RF	7mm x2: OCP207;	The double kit includes two OsteoCool™ RF Ablation
Ablation Dual	OCP207-INT	Probes and two OsteoCool™ Tube Kits.
Probe Kit	10mm x2: OCP210;	
4 different sizes	OCP210-INT;	
	15mm; OCP215;	
	OCP215-INT	
	20mm x2: OCP220; OCP220-INT	
OsteoCool™	OCN001; OCN001-	Allows for optional temperature monitoring around
Independent	INT	the ablation zones to ensure that there is no
Thermocouple		inadvertent damage to adjacent critical structures
28 G (20G cannula)		during the procedure.
OsteoCool™ Bone	10G 090: OCN002	Is a sterile, single use device that is intended for
Access Kits	8G 090: OCN003	percutaneous access to bone. OsteoCool™ Bone
	10G 095: OCN004	Access Kits include one Osteo Introducer (Cannula and
	13G 100: OCN005	Trocar Tip Stylet) and a color-marked OsteoCool
		Precision Drill.

#MDT16075 Version 4.0 Page 28 of 81

## 7.3. Packaging

The OsteoCool™ RF Ablation Probe kit components are supplied sterile packed for single-use. Components should only be accepted if received by the hospital or surgeon with the factory packaging and labeling intact. Once the seal on the sterile package has been broken, the product should not be resterilized or reused. Labeling is specific to the geography and in accordance with local regulations.

## 7.4. Intended Population

The OsteoCool™ RF Ablation system is indicated in the US, EUR and CAN for patients with metastatic malignant lesions in a vertebral body, painful metastatic lesions involving bone (in the US, patients with metastatic lesions involving the bone must have failed or were not candidates for standard therapy) and benign bone tumors such as osteoid osteomas.

Standard therapy is defined per relevant medical society guidelines on treatment of metastatic lesions involving bone. For guidance, please refer to applicable medical society guidelines.

Candidates suitable for RF ablation procedures with the OsteoCool™ RF Ablation System include

- Patients experiencing significant pain from metastases involving bone
- Patients with localized pain resulting from not more than two sites of metastatic disease
- Patients that do not have evidence of impending fracture

The OsteoCool™ RF Ablation System is contraindicated for the use in patients with heart pacemakers or other implanted electronic devices (Europe and Canada only), and for the use in vertebral body levels C1-C7.

All devices used in this study are commercially available and will be used within the intended approved indication as listed in the IFUs for the applicable countries/regions. Any future approved models may be used in the study if commercially available and if the modifications do not have the potential to affect the study results.

### 7.5. Equipment

The Medtronic OsteoCool™ RF Ablation system will be required for this study. The Generator verifies calibration integrity during the Power-On-Self-Test (POST). Maintenance is not required.

#MDT16075 Version 4.0

Page 29 of 81

#### 7.6. Product Use

The OsteoCool™ RF Ablation system will be used according to the standard surgical techniques. The operating surgeon should refer to the respective products' IFU for any corresponding product information prior to using the product.

While not required by the study protocol, the physician may decide that cementoplasty (i.e., Vertebroplasty or Kyphoplasty) is required after the ablation procedure. This information will be collected during the procedure and during any subsequent follow-up procedures.

### 7.7. Product Training Requirements

Physicians performing the RF ablation study procedure should have undergone standard product training by Medtronic on the proper use of its commercially available device prior to initiating the clinical study. Participating physicians must have performed  $\geq 5$  RF ablation procedures that involved either the bone and/or the vertebral body (not necessarily with the OsteoCool product) and  $\geq 2$  procedures with the Medtronic OsteoCoolTM RF Ablation system to participate in the OPuS One clinical study.

### 7.8. Product Receipt and Tracking

This is a post-market study and the OsteoCool™ RF Ablation system used during the study is commercially available. Product receipt and tracking is not required as the devices used during the study are purchased through normal commercial channels.

### 7.9. Product Storage

Products should be stored per the institutions' standard procedures.

#### 7.10. Product Return

Products should be disposed of or returned per the institutions' standard procedures.

### 7.11. Product Accountability

Product accountability is not required for this post-market study as the devices used during the study are purchased through normal commercial channels and maintained per the institutions' standard procedures.

#MDT16075 Version 4.0

Page 30 of 81

### 8. Selection of Subjects

### 8.1. Study Population

Up to 250 subjects that meet eligibility and provide written informed consent will be enrolled into this study. Subjects will be enrolled in approximately 20 centers in the US, EUR, and CAN. Each center can enroll no more than 50 subjects without prior Medtronic approval.

## 8.2. Subject Enrollment

Patients planning to undergo OsteoCool RF ablation will be screened for eligibility to participate in the study. Subjects will be considered enrolled in the study once the informed consent form is signed; however, those who do not undergo the OsteoCool RF ablation procedure (e.g. RF therapy was not delivered) or did not meet the Inclusion/Exclusion criteria will be exited from the study.

#### 8.3. Inclusion Criteria

In order to be eligible to participate in the study, a subject must meet all the following inclusion criteria:

- 1. Candidate for OsteoCool RF ablation per the labeled indication applicable in their respective country/region
- 2. A. Metastatic lesions targeted for treatment must be located in the thoracic and/or lumbar vertebral body(ies), periacetabulum, iliac crest, and/or sacrum OR benign bone tumors no restrictions on location of lesion.
- 3. Report worst pain score ≥4/10 at the target treatment site within the past 24 hours
- 4. Localized pain resulting from not more than two sites of metastatic disease
- 5. Have Karnofsky score ≥40 at enrollment (not applicable for subjects with benign bone tumors)
- 6. Willing and able to provide a signed and dated informed consent, comply with the study plan, follow up visits and phone calls
- 7. At least 18 years old at the time of informed consent

#### 8.4. Exclusion Criteria

A potential subject who meets any of the following criteria will be excluded from participating in the study:

- 1. A. Implanted with heart pacemaker or other implanted electronic device (Europe and Canada only)
- 2. Use of OsteoCool in vertebral body levels C1-C7
- 3. Multiple myeloma, solitary plasmacytoma, or primary malignant lesions in the index vertebra or bone.
- 4. Active or incompletely treated local infection at the planned treatment site(s) and/or systemic infection
- 5. Planned treatment site(s) accompanied by objective evidence of secondary radiculopathy or neurologic compromise

#MDT16075 Version 4.0 Page 31 of 81

- 6. Planned treatment site(s) associated with spinal cord compression or canal compromise requiring decompression
- 7. Fractures due to prostatic cancer or other osteoblastic metastases to the spine. Metastatic lesions originating in the prostate that are osteolytic or of mixed origin are eligible for the study
- 8. Pregnant, breastfeeding, or plan to become pregnant during the study duration
- Concurrent participation in another clinical study that may add additional safety risks and/or confound study results\*
- 10. Any condition that would interfere with the subject's ability to comply with study instructions or might confound the study interpretation

### 9. Study Procedures

### 9.1. Schedule of Events

The study schedule, procedures, and methods of assessment are defined in detail to enable compliance with the required activities, and to ensure that the resulting data meet the criteria for evaluability. See Figure 6-1 and Table 9-1 for visit requirements. A table listing protocol visit windows is presented in Table 9-2. The pertinent electronic Case Report Forms (eCRFs) along with the applicable source documentation will be completed for each subject.

#### 9.1.1. Enrollment

Subjects are considered enrolled at the time the study-specific IC is signed.

#### **9.1.2.** Baseline

The Enrollment and Baseline visits can occur on the same day. Each subject must meet all of the inclusion criteria and no exclusion criteria to be eligible to continue participation in this study. Informed Consent must be signed prior to any study-related procedures.

The following information will be collected at the baseline visit:

- Verification of Inclusion/Exclusion criteria
- Pregnancy test for women of child-bearing potential
- Karnofsky Performance Scale (not applicable for subjects with benign bone tumors) (refer to section 9.6.3)
- Method by which focal pain was correlated with treatment site (e.g., imaging, physical examination)
- Demographics (refer to section 9.6.2)
- Collection of pre-treatment images (e.g., MRI, PET, etc.) relevant to the targeted site(s), US and CAN only, if available
- Disease characteristics (refer to section 9.6.4)

\*Subjects in concurrent studies can only be enrolled with permission from Medtronic. Please contact Medtronic's study manager to determine if the subject can be enrolled in both studies.

#MDT16075 Version 4.0 Page 32 of 81

- Prior and concomitant cancer and/or tumor treatments relevant to the targeted site(s), if applicable (refer to section 9.6.6)
- Prior and concomitant pain medications (refer to section 9.6.6)
- BPI includes worst pain score in the past 24 hours at the target treatment site (refer to section 9.6.1)
- EQ-5D-5L (refer to section 9.7.9)
- EORTC QLQ-C15-PAL (not applicable for subjects with benign bone tumors) (refer to section 9.7.10)
- Reportable adverse events/device deficiencies/deviations (refer to section 11 and section 9.10)

Note: When possible, the follow up visits, questionnaires and data collection should be scheduled at least 72 hours after chemotherapy and/or radiation treatment.

#### 9.1.3. OsteoCool Procedure (Day 0)

Enrollment, Baseline and RF ablation can occur on the same day. OsteoCool Procedure must occur ≤21 days after the baseline visit. Informed Consent must be signed prior to any study-related procedures.

The following information will be collected during the OsteoCool RF ablation procedure visit:

- Location of each treated site
- Concomitant cancer and/or tumor treatments, relevant to the target site(s), if applicable (refer to section 9.6.5)
- Concomitant pain medications (refer to section 9.6.6)
- OsteoCool procedure data (per lesions treated)
- OsteoCool generator data uploads
- Use of Cementoplasty (i.e., Vertebroplasty or Kyphoplasty)
- PI assessment of local tumor control optional
- Reportable adverse events/device deficiencies/deviations (refer to section 11 and section 9.10)

Follow the detailed procedures and instructions found in the applicable Instructions for use.

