#### 9.6.6. Prior and Concomitant Medications

There are no restrictions to prior or concomitant medications before or during the study. The specific concomitant medications listed below should be documented as concomitant medications and will be updated at each visit:

- **Osteoporosis medication(s):** Antiresorptive medications (e.g., bisphosphonates, parathyroid hormone (PTH), calcitonin), calcium, and vitamin D.
- **Steroid(s):** any steroid use, including steroid inhalers
- **Oral narcotics in last 24 hours.** This information will be converted to oral morphine equivalent dose (OMED) (including transdermal patches)

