#### 13.3.4. Endpoint Definition

Change in pain will be calculated as:

 $\mu_c$  = worst-pain 3-month – worst-pain baseline

A negative value for change in pain represents a lowering of the subject's pain score (an improvement, or reduction in pain) and a positive value represents an increase in the subject's pain score (a worsening, or increase in pain).

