#### 13.3.5. Sample Size Methods and Assumptions

The standard deviation of change from Greenwood et al (2015) is estimated to be 4.1 at 4 weeks. The standard deviation of change in the CAFE study Berenson et al (2011) was 3.2 at 1 month. The standard deviation of change from Lane et al (2011) is estimated to be 2.4 at 1 day post-procedure. It is not known which of those studies will most closely match the population and test conditions in this study. The median of those 3 studies is 3.2. To account for this study having a longer follow-up period and a more diverse patient population, and thus more opportunity for variability, the standard deviation for our sample size calculation will be increased to 3.5.

The minimal clinically important difference (MCID) of 2 points was used to interpret pain score differences in terms of clinical relevance in Bagla et al (2016) and a clinically significant change in pain of 2 points was also identified in Greenwood. This will be used for our calculations.

Bagla followed subjects for 3 months post procedure. They reported that pain scores were provided for 68% of subjects (32% not provided) at 3 months. This will be used for our calculations.

The PASS program used to calculate the sample size was the one-sample t-test power analysis, mean0=0, meanA=2, standard deviation (of change) =3.5, two-sided significance level (alpha)=0.05, and power=0.90. The required sample size was 35. To account for subjects getting treated but not providing the 3-Month data, the treated sample size is adjusted for a 32% loss, to 52.

#MDT16075 Version 4.0

Page 58 of 81

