#### 13.3.6. Analysis Methods

A two-sided t-test with alpha=0.05 will be used to test the null hypothesis of no change in worst-pain score between baseline and 3 months.

If the distribution of the change scores does not meet the assumption of normality, the non-parametric Wilcoxon signed-rank test will be used to test for significant change with alpha=0.05, two-sided.

The primary objective hypothesis will be tested after the sample size requirements for it have been met. If additional subjects are enrolled later and also treated for metastatic lesions involving only the vertebral body, those additional subjects will be combined with the first group and summarized together.

The main analysis for the primary objective hypothesis testing will be on the Completers population.

In order to include all the treated subjects in the analysis, a sensitivity analysis will be performed on the Treated population. The endpoint data will first undergo multiple imputations (MI). Rather than filling in a single value for each missing value, MI replaces each missing value with a set of "plausible" values that represent the uncertainty about the correct value to impute. These multiple imputed datasets are then analyzed using standard statistical procedures and then combined into one analysis result with an appropriately increased variance. Included in the MI analysis will be the endpoint variable at 3 months and the endpoint variable at baseline, 3 days, 1 week, 1 month, and unscheduled visits (if collected), as well as baseline covariates. The method to be used is the Markov chain Monte Carlo (MCMC) method of SAS (version 9.4 or higher). This is an iterative method that can be used when the pattern of missing data is arbitrary (monotone or non-monotone). The default number of iterations will be used (n=5) and, if needed, will be increased until the Markov chain converges.

A single imputation method will also be performed, substituting the Treated population's endpoint variable at the last available follow-up (Bagla) for the missing endpoint variable.

Sensitivity analyses will be performed, separating the evaluation by whether or not the subjects received vertebral augmentation procedures and/or post RFA radiation therapy.

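### The primary change score starts from a baseline-visit pain score taken up to 21 days before ablation, with no pre-ablation score on Day 0, so earlier pain change in either direction is counted as part of the device's before-after change

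*Combined protocol and SAP*

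**What the plan says.** Inclusion criterion 3 (CIP 8.3) reads "Report worst pain score ≥4/10 at the target treatment site within the past 24 hours". CIP 9.1.2 lists both the eligibility check and the BPI worst-pain item at the baseline visit, for the same site and the same 24-hour window.

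On timing, CIP 9.1.3 says "OsteoCool Procedure must occur ≤21 days after the baseline visit". It also allows enrolment, baseline and ablation on one day. Its Day 0 list includes pain medication and target-site cancer treatment but no pain score. In Table 9-1 the BPI row has no mark under Day 0, and the row for worst pain alone is marked only before discharge. The next score after baseline is therefore taken after ablation (CIP 9.1.4).

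On what may happen in between, CIP 9.6.6 says "There are no restrictions to prior or concomitant medications before or during the study". CIP 9.6.5 records treatment at the target site but does not limit it.

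The endpoint (CIP 13.3.4, SAP 7.9.1) is the 3-month score minus the baseline score. The analysis is: "A two-sided t-test with alpha=0.05 will be used to test the null hypothesis of no change in worst-pain score between baseline and 3 months". Neither document defines baseline as the last value before the procedure. The sensitivity analyses in CIP 13.3.6 and SAP 7.9.1 deal with missing data and, in the CIP, with vertebral augmentation and radiation given after ablation. None deals with the baseline-to-procedure interval or with treatment started before ablation.

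**The concern.** With no control arm, the starting score is the only reference the study has. Two separate things are mixed into it.

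1. **Change before ablation.** A subject scored three weeks early may start an opioid, a steroid or radiation, or may progress, before being treated. Whatever happens to pain in that time becomes part of the before-after change. Subjects scored on the day of treatment are pooled with subjects scored up to 21 days earlier as if the two baselines meant the same thing.
2. **Selection.** If the score that admits the patient is also the starting point, a patient admitted on an unusually bad day will tend to score lower later without any treatment. This needs no gap; it applies to same-day baselines too.

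What is at stake is mainly the size of the reported improvement. CIP 4.2 says the data may serve regulatory, reimbursement and clinical needs, and for those uses the size matters as well as the p-value.

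**Working it through.** **Step 1. The plan's own sample size.** Inputs from CIP 13.3.5: mean change 2 (the clinically important difference), SD of change 3.5 ("the standard deviation for our sample size calculation will be increased to 3.5"), two-sided alpha 0.05, power 0.90, loss 32%. Exact one-sample t-test power uses the noncentral t with n − 1 degrees of freedom and noncentrality (2/3.5)·√n.

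- n = 34 gives 89.9% and n = 35 gives 90.7%, so 35 is reproduced.
- 35/(1 − 0.32) = 51.5, rounded up to 52, which is also reproduced.
- The smallest significant mean change at n = 35 is t(0.975, 34)·3.5/√35 = 1.20 points.

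The arithmetic of the plan is not in question.

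**Step 2. Change before ablation.** If a share p of subjects have an earlier baseline and their mean pain moves by d before Day 0, the primary mean shifts by p·d. The documents give neither p nor d, so this shows only what a given overall shift would do (n = 35, SD 3.5).

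| Overall shift (points) | Pain fell before ablation, no device effect: chance of p<0.05 | Pain rose before ablation, true device effect 2 points: power |
|---|---|---|
| 0.25 | 7.0% | 82% |
| 0.50 | 13.0% | 69% |
| 0.75 | 23.4% | 54% |
| 1.00 | 37.6% | 38% |

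The last column is the power for a net change of 2 minus the shift. The error can run for or against the device.

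**Step 3. Regression to the mean from the entry rule.** Assumed, not in the documents: screened worst pain has mean m, SD s = 2.5 and retest correlation r. A rounded score of at least 4 corresponds to a cut at 3.5. With a = (3.5 − m)/s, the expected fall on remeasurement without treatment is (1 − r)·s·φ(a)/(1 − Φ(a)).

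- m = 5, r = 0.5: a = −0.6; 0.5 × 2.5 × 0.3332/0.7257 = 0.57.
- m = 6, r = 0.6: a = −1.0; 0.4 × 2.5 × 0.2420/0.8413 = 0.29.
- m = 7, r = 0.8: a = −1.4; 0.2 × 2.5 × 0.1497/0.9192 = 0.08.
- m = 8, r = 0.6: a = −1.8; 0.4 × 2.5 × 0.0790/0.9641 = 0.08.

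Simulating 2,000,000 pairs of scores rounded to 0–10 gives 0.58, 0.29 and 0.09 for the first three cases. The middle case is about 15% of the 2-point difference (0.29/2).

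At n = 35 and SD 3.5, the chance of p<0.05 with no treatment effect is 15.9%, 7.7% and 5.2% for those three cases. Wider assumptions (mean 4 to 7, SD 2.0 to 2.5, correlation 0.4 to 0.8) give a fall of 0.04 to 1.0 points and a rejection rate of 5% to 38%.

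**Step 4. Against the effect the plan expects.** The prospective spinal ablation series summarised in CIP 4.4 fell from 5.9 to 2.1, or 3.8 points. Taking off 0.3 leaves 3.5. At n = 35 and SD 3.5 the noncentrality is (3.5/3.5)·√35 = 5.9, and power exceeds 99.9%.

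**The case against.** Several counter-arguments have force.

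- **Direction.** A reader might infer that the 21-day gap always flatters the device. The documents do not support that. These are mostly patients with metastatic disease, CIP 13.1.4 itself expects deteriorating health, and progression before Day 0 would count against the device. Only the entry rule has a known direction.
- **Source of the figure.** A reader might attribute the 0.1 to 0.6 points to the gap. It comes from the entry rule and does not depend on the gap. The drift in the gap cannot be sized from the documents.
- **One score or two.** The protocol never says that the recorded BPI item is the qualifying score, and CIP 9.2 also has eligibility reviewed at screening. That they are the same is an inference from the same visit, site and time window; no separate qualifying score is scheduled.
- **Size.** Pre-treatment values in other series cited in CIP 4.4 are a mean of 8.4 and a median of 8. If the screened mean were 8 to 8.4, regression to the mean at r = 0.6 would be only 0.06 to 0.09 points. The rejection rates also combine the plan's SD of 3.5 with assumptions that imply an SD of change of about 1.5 to 2.3; using the implied SD would raise the rates.
- **Mitigation.** Pain medication and target-site treatment are recorded at both baseline and Day 0, and the response definition in CIP 9.6.7 takes opioid dose into account. The Additional Measures sections are blank in this copy, so a relevant analysis there cannot be ruled out.

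These points limit the size and the certainty of the concern. They leave standing that no score is scheduled on Day 0 before ablation, and that the stated primary and sensitivity analyses do not deal with it.

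**Conclusion.** The concern holds as a bias in the estimated change. For subjects whose baseline precedes Day 0, pain change before ablation is inseparable from change after it. Its direction and size are unknown from the documents. Regression to the mean adds an apparent improvement of about 0.1 to 0.6 points under a screened mean of 5 to 7, SD 2.5 and correlation 0.5 to 0.8, and under about 0.1 points at a mean of 8 or more with r = 0.6. All of these inputs are assumed, so this is a range and not an estimate.

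A reader might conclude that the primary test is invalid or likely to give a false positive. The documents do not support this: the sample size reproduces, and a fall like that in the cited spinal series would remain clearly significant after subtracting the bias. The change is worth making because it is cheap and improves the figure the study exists to report. It does not replace a control for what happens after Day 0.

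**What to change.** 1. **CIP 9.1.3 and Table 9-1.** Add the single worst-pain item (target site, last 24 hours) on Day 0, before sedation and ablation, when the baseline visit was on an earlier day. A same-day repeat would cover nearly the same 24 hours and is not worth asking.
2. **CIP 13.3.4 and SAP 7.9.1.** If the amendment precedes enrolment of the primary cohort, define baseline as the last pre-procedure score. Otherwise keep the baseline-visit score for the primary test, so that about 35 completers do not mix two endpoint definitions, and add a prespecified sensitivity analysis of change from the last pre-procedure score.
3. **Subjects without a Day 0 score.** Report change by same-day versus earlier baseline, and by whether target-site treatment or pain medication recorded on Day 0 differs from that at baseline. Finer interval groups would be too small. Comparing the two records avoids relying on treatment start dates, which CIP 9.6.5 does not specify.

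Cost: one extra question at an existing visit, a short amendment and some SAP wording. The reported improvement may be slightly smaller, and regression to the mean is not removed for same-day baselines. The 35 and 52 stand if the 2-point difference and SD 3.5 are kept.
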